3.3 General Quinacrine Information

Quinacrine:

Convulsive seizures have occurred in patients receiving quinacrine and corticosteroids concomitantly [62]. Concurrent use of primaquine with quinacrine may inhibit the metabolism of Primaquine or may displace it from tissue-binding sites, thereby increasing serum concentrations and potential toxicity of primaquine. These effects may last for up to 3 months after the last dose of quinacrine is administered. Therefore concurrent use of quinacrine and primaquine is contraindicated) [47, 51]. Since quinacrine concentrates in the liver, it should be used with caution in conjunction with hepatotoxic drugs and in patients with hepatic disease or alcohol dependence [51]. Alcohol, or alcohol-containing medication, is not recommended during quinacrine treatment (quinacrine has been reported to produce a mild Disulfram-like reaction when ingested with alcohol, which may be due to quinacrine's inhibition of the intermediary metabolism of alcohol; ingestion of alcohol or alcohol containing medication is not recommended during quinacrine treatment) [51].

Pregnancy/Lactation: FDA Pregnancy Risk Category C: Quinacrine should not be given to pregnant women because the drug readily crosses the placenta and reaches the fetal circulation system [52]. There is one case of possible renal agenesis and hydrocephalus in an infant, although normal pregnancies have been reported after quinacrine ingestion during the first 4 weeks of gestation [63]. Adequate, well-controlled human studies are lacking, and animal studies have shown a risk to the fetus or are lacking as well. There is a chance of fetal harm if the drug is given during pregnancy; but the potential benefits may outweigh the potential risk [63]. Quinacrine was embryo lethal but not teratogenic in rats administered intrauterine quinacrine and gestation day 8 or day 12 [64]. A small amount of quinacrine is excreted in breast milk. However, problems in humans have not been documented [26].

3.4 General Capecitabine Information

Capecitabine:

Capecitabine should be administered within 30 minutes after a meal. Capecitabine and/or its metabolites may inhibit cytochrome P-450 (CYP) 2C9 isoenzyme, and therefore increase levels of substrates of CYP2C9: Because the decreased rate of anticoagulant metabolism may increase patient response to coumarin and indandione derivatives, capecitabine and these agents should be used concomitantly with great caution [23]. If capecitabine is used concomitantly with a coumarin anticoagulant, prothrombin time (PT) or international normalized ratio (INR) should be monitored frequently, and the anticoagulant dose should be adjusted accordingly. Concomitant use of phenytoin and capecitabine, serum concentrations of phenytoin must be monitored carefully, and reduction in the phenytoin dosage may be necessary [23]. Concomitant use of folic acid may affect the metabolism of capecitabine [23]. Leucovorin (LV) potentiates the antineoplastic activity of 5-FU and also may increase its toxicity. Deaths from severe enterocolitis, diarrhea, and dehydration have been reported in geriatric patients receiving a weekly regimen of combination therapy with LV and 5-FU [23].

Pregnancy/Lactation: FDA Pregnancy Risk category: Studies in humans, or investigational or postmarketing data, have demonstrated fetal risk. Nevertheless, potential benefits from the use of the drug may outweigh the potential risk. For example, the drug may be acceptable if needed in a life threatening. In lactating mice receiving a single dose of capecitabine, significant amounts of capecitabine metabolites were distributed into milk. Because of the potential for serious adverse reactions to capecitabine in nursing infants, nursing should be discontinued during capecitabine therapy.

Dose adjustments: For mild renal dysfunction (creatinine clearance 30-50 mL/min), it is recommended to reduce dose by 25%. For severe renal dysfunction (creatinine clearance <30 mL/min), treatment is not recommended. For elderly patients, lower doses may be required due to higher incidences of serious adverse reactions.

3.5 Duration of therapy

Treatment continues until at least one of the following criteria applies:

- Disease progression,
- Intercurrent illness that prevents further administration of treatment,
- Unacceptable adverse event(s) (DLT)
- Patient decides to withdraw from the study, or
- General or specific changes in the patient's condition render the patient unacceptable for further treatment in the judgment of the investigator.

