*NA indicates that the action taken is the same regardless of whether there were patients previously treated at a higher dose

The MTD will be used at recommended phase 2 dose (RP2D) unless there are any safety concerns. Patients who needed a dose reduction after being treated with RP2D in phase I will receive the reduced dose in phase II.

For the purposes of quinacrine dose escalation, the dose-limiting toxicities (DLT) that will be taken into account include toxicity grade >2 hematological, GI/diarrhea, skin, LFT abnormality or otherwise unexpected grade 3 toxicity or higher, associated with the combination therapy. Quinacrine dose modifications will not be made in the event of toxicities that are primarily attributed to capecitabine; namely, > grade 2 alopecia and hand and foot syndrome (HFS). Patients experiencing DLT will be permitted to continue their treatment after a single step dose reduction.

Intra-patient dose escalation will occur only for patients experiencing Common Toxicity Criteria < grade 2 toxicity on a previous course. The intra-patient dose escalation for a patient in lower level dose cohort will be on hold until the highest dose cohort patient completes first cycle of therapy. For purposes of toxicity assessment, patient response to the initial dose received will be considered. Total time in therapy, however, will be adjudged to include the whole duration the patient received treatment, regardless of the doses received.

General concomitant medications, dose adjustment, drug warnings and supportive care guidelines, duration of therapy, duration of follow up, and criteria for removal from treatment, as described throughout the protocol will be applied to both Phase I and II.

The endpoint of the Phase I portion of this study will occur when the safety and tolerability of the quinacrine-capecitabine combination is evaluated. Based on our preclinical data and the history of use of both capecitabine and quinacrine, we expect that the following regimen will be safely tolerated by the majority of patients.

	Premedications;				Cycle
Agent	Precautions	Dose	Route	Schedule	Length
Quinacrine	After a meal with a	200 mg tablets	Orally:	Daily on	
	glass of water	Orally twice a	at least 8 hours	Days 1-21	
		day	between each		
			dose		
Capecitabine*	Within 30 minutes	1000 mg/m ²	Orally:	Daily on	21 days
	after a meal with	Orally twice a	at least 8 hours	Days 1-14	(3 weeks)
	water	day	between each		
			dose		

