3.2 Phase II

An open label, single stage design will be used in the Phase II portion of this study. The treatment outlined in the previous section, using RP2D derived from Phase I, will be administered on an outpatient basis. The patient will be requested to maintain a medication diary of each dose of medication. The medication diary will be returned to clinic staff at the end of each cycle. Reported adverse events and

potential risks of quinacrine and capecitabine are described in Section 6. Appropriate dose modifications for quinacrine and capecitabine are described in Section 5. No investigational or commercial agents or therapies other than those described below may be administered with the intent to treat the patient's malignancy.

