3.7 Criteria for removal from treatment

Patients will be removed from treatment when any of the criteria listed in Section 3.5 applies. The reason for removal from treatment and the date the patient was removed must be documented in eCRF system.

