5.0 Treatment Modifications

5.1 Dose Reductions

In the event of alopecia, HFS, or stomatis, only capecitabine dose will be reduced according to the following table.

Hand and Foot	Management/Next Dose for Capecitabine		
Syndrome/Stomatitis/Alopecia			
Grade 1	No change in dose		
Grade 2	Hold until \leq Grade 1. Resume at same dose level.		
Grade 3	Hold until < Grade 1. Resume at one dose level lower, if		
Glade 5	indicated. (Per Section 5.2 Dose Levels)		
Grade 4	Off protocol therapy		

In the event of other toxicities that are specifically attributable to capecitabine (such as hand-foot syndrome, diarrhea), the dose of capecitabine will be delayed or reduced first. If toxicity progresses or does not improve within 72 hours after capecitabine delay or reduction, quinacrine will also be delayed/ dose-reduced. Dosing delays/modifications will be done according to the following schema:

Diarrhoa	Management/Next Dose for	Management/Next Dose for	
Diamiea	quinacrine	capecitabine	
Grade 1	No change in dose	No change in dose	
	Hold until \leq Grade 1. Resume at	Hold until \leq Grade 1. Resume at	
	same dose level.	same dose level. If it reoccurs, hold	
Grade 2		until < Grade 1 and resume at one	
		dose level lower. (Per Section 5.2	
		Dose Levels)	
	Hold until < Grade 1. Resume at	Hold* until < Grade 1. Resume at	
Grade 3	one dose level lower, if indicated.	one dose level lower, if	
Clauc 5		indicated.** (Per Section 5.2 Dose	
		Levels)	
Grade 4	Off protocol therapy	Off protocol therapy	
Recommended management: Loperamide antidiarrheal therapy			
Adjunct anti-diarrheal therapy is permitted and should be recorded when used.			

All other toxicities	Management/Next Dose for	Management/Next Dose for	
All other toxicities	quinacrine	capecitabine	
Grade 1	No change in dose	No change in dose	
Crada 2	Hold until \leq Grade 1. Resume at	Hold until \leq Grade 1. Resume at	
Grade 2	same dose level.	same dose level.	
	Hold until < Grade 1. Resume at	Hold until < Grade 1. Resume at	
Grade 3	one dose level lower, if indicated.	one dose level lower, if indicated.	
		(Per Section 5.2 Dose Levels)	
Grade 4	Off protocol therapy	Off protocol therapy	

Recommended management for nausea: antiemetics

If treatment needs to be held for more than 3 weeks due to severe treatment related toxicities that cannot be resolved despite maximum supportive care, the patient will be taken off protocol therapy.

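### After a grade 3 DLT, Sections 3.5 and 3.7 remove the patient from treatment, while Sections 3.1 and 5.1 let the same patient resume at a reduced dose

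*Combined protocol and SAP*

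**What the plan says.** Section 3.5 (Duration of therapy) gives a list of events, any one of which ends treatment. One entry is "Unacceptable adverse event(s) (DLT"). Section 3.7 adds: "Patients will be removed from treatment when any of the criteria listed in Section 3.5 applies". It gives no exception.

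Section 3.1 (Phase I) defines the term: "For the purposes of quinacrine dose escalation, the dose-limiting toxicities (DLT) that will be taken into account include toxicity grade >2 hematological", followed by further organ categories and then "otherwise unexpected grade 3 toxicity or higher, associated with the combination therapy". Grade 3 events are therefore DLTs. The same section says: "Patients experiencing DLT will be permitted to continue their treatment after a single step dose reduction". That permission carries no upper grade limit.

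Section 5.1 (Dose Reductions) grades the response. In the diarrhea table and the table for all other toxicities, a grade 3 event leads to an interruption and then a restart at "one dose level lower, if indicated". Coming off protocol therapy is kept for grade 4, or for an interruption longer than 3 weeks because of severe related toxicity that does not resolve.

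On scope, Section 3.1 says that dose adjustment and "criteria for removal from treatment, as described throughout the protocol will be applied to both Phase I and II". Section 3.2 (Phase II) says: "Appropriate dose modifications for quinacrine and capecitabine are described in Section 5".

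**The concern.** The same patient meets two instructions that cannot both be followed. Read literally, Sections 3.5 and 3.7 take a patient with a grade 3 DLT off treatment. Section 3.1 (in Phase I) and the grade 3 rows of Section 5.1 allow that patient to be treated again at a lower dose.

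What is at stake is re-exposure after a serious toxicity. It would depend on which section the investigator happens to follow, so comparable patients could be managed differently. Section 3.7 also requires the reason and date of removal to be recorded, and that record is consistent only if there is one rule. No effect on efficacy, power or the toxicity-halting probabilities is claimed.

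**Working it through.** **1. One patient, four sections.** Take a patient with grade 3 diarrhea associated with the combination. Section 3.1 names this category, so the event is a DLT.

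| Section | Consequence |
|---|---|
| 3.5 with 3.7 | Removed from treatment |
| 3.1 (Phase I) | May continue after one dose reduction |
| 5.1, grade 3 row | Interrupt, then resume one level lower if indicated |
| 5.1, off-therapy triggers | Not met unless grade 4 or an interruption over 3 weeks |

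The qualifier in the grade 3 row gives discretion over the reduction. It does not require removal.

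**2. By grade.** At grade 3 the conflict is direct. At grade 4, Sections 3.5 and 5.1 agree, and only the ungraded permission in 3.1 is out of line. The hand-foot syndrome, stomatitis and alopecia table is left aside, because 3.1 attributes alopecia and hand-foot syndrome above grade 2 mainly to capecitabine.

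**3. By phase.** In Phase I the conflict is explicit: 3.5 and 3.7 against 3.1 and 5.1. In Phase II it is an inference: 3.5 and 3.7 against 5.1. The inference has three supports. Section 3.1 applies both the removal and the dose-adjustment rules to both phases, Section 3.2 sends Phase II to Section 5, and Section 11.1 uses the term DLT in Phase II without redefining it.

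**4. The plan's own DLT figures.** Section 11.1 halts Phase II at 5 DLTs in the first 10 patients or 8 in 29. An exact sequential binomial calculation gives a halting probability of 0.805 at a true rate of 33.3% (stated 80.5%) and 0.063 at 15% (stated 6.3%). Both reproduce. Neither depends on what treatment follows a DLT.

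**5. How often the Phase II conflict could arise.** Let p be the DLT rate and s the share of DLT patients whose DLT is grade 3 only. The documents give no value for s, so 25%, 50% and 75% are assumptions; s = 1 is the ceiling. Patients are taken as independent. The rates p are those of the Section 11.1 toxicity rule, not forecasts. The probability of at least one such patient among the first 10, with halting at 5 DLTs, is:

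| p | s = 0.25 | s = 0.50 | s = 0.75 | s = 1 |
|---|---|---|---|---|
| 15% | 31.8% | 54.1% | 69.7% | 80.3% |
| 33.3% | 57.6% | 83.7% | 94.4% | 98.3% |

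The last column is 1 − 0.85^10 = 0.803 and 1 − (2/3)^10 = 0.983. Ignoring the halting rule, 1 − (1 − p·s)^10 differs by at most 0.006; for example, at p = 1/3 and s = 0.25 it gives 0.581 against 0.576.

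These figures cover only the first 10 patients. Carried through 29 patients with the same halting rule and ignoring the futility stop, s = 0.25 gives 66.8% and 85.5%, and s = 1 gives 99.1% and over 99.9%. On the same basis, the expected number of Phase II patients with a DLT of any grade is the rate times the expected enrolment: 0.15 × 28.63 = 4.3 and (1/3) × 20.99 = 7.0.

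**The case against.** The strongest reply is that Section 3.5 is a short summary list and the word unacceptable still limits it. On that reading the entry covers only the off-therapy triggers of Section 5.1, and Sections 3.1 and 5.1 supply the working detail. Section 3.6 gives some support, since it speaks of removal for unacceptable adverse events without mentioning DLT. Section 3.1 also applies the dose-adjustment and removal rules together, which suggests they were meant to work jointly. This reading is possible, but no passage states it. The parenthesis in 3.5 points the other way, because it ties the entry to a term that 3.1 defines to include grade 3. The last entry in the 3.5 list expressly reserves investigator judgment; the DLT entry does not.

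A second reply is that the DLT definition is given for quinacrine dose escalation, and that Section 11.1 uses DLT in Phase II only to count events for halting the trial. That stands, and it is why the Phase II conflict is called an inference.

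A third is that the capecitabine cell for grade 3 diarrhea carries footnote marks, and the footnotes are absent from the text that was available. They might qualify resumption in that cell. The quinacrine diarrhea cell and both grade 3 cells for all other toxicities carry no such marks, so the contradiction does not depend on the footnotes.

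Finally, the frequency figures rest on assumed grade shares and are not needed to establish the point. That is correct; they only indicate that the case is unlikely to be rare.

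**Conclusion.** The concern holds. For a grade 3 DLT the protocol gives incompatible instructions, explicitly in Phase I and by inference in Phase II, and nothing ranks them. At the protocol's own design rates, the ceiling on the chance that the conflict arises at least once in the first 10 Phase II patients is 80.3% to 98.3%. The actual chance depends on the grade mix, which the documents do not give, and it rises if Phase II runs to 29 patients. The consequence is inconsistent individual management after a DLT. The stated halting probabilities are unaffected. This should be fixed, but it does not undermine the design.

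**What to change.** Reconcile Sections 3.1, 3.5, 3.7 and 5.1 so that one rule, set out by grade and by phase, states what follows a DLT. The amendment should:

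- say whether the DLT label in 3.5 means every DLT or only the off-therapy triggers in 5.1;
- say whether the Phase I permission in 3.1 has a grade limit, since it now differs from 5.1 at grade 4;
- say whether the DLT definition in 3.1 also applies in Phase II;
- cover the case in Section 5.2 where the recommended Phase II dose leaves no room for a dose reduction.

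Which clinical rule applies is for the sponsor to decide. The cost is a wording amendment, with no extra patients, procedures or data.

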3.6 Duration of follow-up

Patients will be followed for five years after removal from treatment or until death, whichever occurs first. Patients removed from treatment for unacceptable adverse events will be followed until resolution or stabilization of the adverse event. We expect that most patients will not require a follow-up of 5 years due to their poor prognosis. However we want to include long time survivors due to the combination of quinacrine treatment with capecitabine. Patients will be followed every 3 months either in clinic or via the telephone. Patients will continue to require tumor measurements every 6-9 weeks per section 10.1 until disease progression.

3.7 Criteria for removal from treatment

Patients will be removed from treatment when any of the criteria listed in Section 3.5 applies. The reason for removal from treatment and the date the patient was removed must be documented in eCRF system.

4.0 PATIENT SELECTION

4.1 Inclusion Criteria

Participants must meet all of the following inclusion criteria:

4.1.1 On primary diagnosis, patients must have had histologically confirmed adenocarcinoma of the colon or rectum. Metastasis or recurrence do not need to be histologically confirmed

- 4.1.2 Standard, curative or palliative measures do not exist or are no longer effective
- 4.1.3 Patients must have measurable recurrence or metastases, per RECIST 1.1
- 4.1.4 Patients must have prior chemotherapy for advanced CRC and have previously received both an oxaliplatin and an irinotecan based regimen. Patients who are not appropriate for second line therapy because of their KRAS mutational status or because they cannot tolerate second line therapy, will be included even after only one prior therapy regimen
- 4.1.5 All prior systemic cancer therapy (hormonal, chemotherapeutic, and immunotherapeutic) must be completed at least 4 weeks before the baseline visit
- 4.1.6 Patients must be at least 4 weeks from radiation therapy or major surgery and have recovered from prior toxicities
- 4.1.7 Age >18 years
- 4.1.8 Life expectancy greater than 3 months
- 4.1.9 ECOG performance status of 0, 1, or 2

4.1.10 Patients must	have normal	organ and	marrow	function a	as defined	below:
1.1.101 0000000000000000000000000000000	ma ve morniar	or gain and	111011011	1411011011	ab actilited	001011.

Leukocytes	>1,500/mcL
Absolute neutrophil count	>1,500/mcL
Platelets	>100,000/mcL
Total bilirubin	<2.5 ULN
AST/ALT	<3.0 ULN
Creatinine	<2.0
Creatinine Clearance*	\geq 50

*Creatinine Clearance must be calculated using Cockroft-Gault formula

- 4.1.11 Patient must be able to swallow capsules
- 4.1.12 Patients must be able to understand and willing to sign a written informed consent document

4.2 Exclusion Criteria

All candidates meeting any of the exclusion criteria at baseline will be excluded from study participation:

4.2.1 Patients may not be receiving any other investigational agents.

- 4.2.2 Patients who have had chemotherapy or radiotherapy 4 weeks or more prior to entering the study who's adverse events have not recovered to grade 1 or less with the exception of alopecia and neuropathy
- 4.2.3 Patients with known brain metastases
- 4.2.4 History of allergic reactions attributed to compounds of similar chemical or biologic composition to quinacrine, capecitabine or fluorouracil.
- 4.2.5 Patients receiving any medications or substances that are substrates, inducers, or inhibitors of CYP2C9 enzyme. For a list of common CYP2C9 substrates, inducers, and inhibitors, see Appendix B
- 4.2.6 Uncontrolled intercurrent illness including, but not limited to, ongoing or active infection symptomatic congestive heart failure, unstable angina pectoris, cardiac arrhythmia, or psychiatric illness/social situations that would limit compliance with study requirements.
- 4.2.7 Pregnant or breast feeding women are excluded from this study
- 4.2.8 Other reasons:
 - Patients currently being treated with quinacrine or drugs related to quinacrine
 - Patients who require anti-arrhythmic treatment with Amiodarone or any drug with a quinidine-like effect on the heart or who have history of a malignant ventricular arrhythmia unless they have a functioning Automatic Implantable Cardio Defibrillator (AICD) implanted.
 - Patients who have a history of noninfectious (toxic, autoimmune) hepatitis or alcoholism.
 - Patients with a lifetime history of porphyria or psoriasis
 - Patients with documented glucose-6-phosphate dehydrogenase deficiency.
 - Patients with a history of seizure disorder (except infant febrile seizures).
 - Patients with a lifetime history of dermatitis as an allergic/toxic reaction to any medication.
 - Patients with known dihydropyrimidine dehydrogenase (DPD)deficiency.

4.3 Inclusion of Women and Minorities

Both men and women and members of all races and ethnic groups are eligible for this trial. However, we will require that women of child bearing potential use adequate contraception during the administration of the study drugs.

4.4 Pregnancy

The effects of capecitabine and quinacrine on the developing human fetus at the recommended therapeutic dose are unknown. For this reason women of child-bearing potential (WOCBP) and men must agree to use adequate contraception (hormonal or barrier method of birth control; abstinence) prior to study entry, for the duration of treatment, and for at least 3 months after the completion of treatment. Should a woman become pregnant or suspect she is pregnant while participating in this study, she must inform her treating physician immediately.

Prior to study enrollment, WOBCP must be advised of the importance of avoiding pregnancy during trial participation and the potential risk factors for an unintentional pregnancy. In additional, men enrolled on this study should understand the risks to any sexual partner of childbearing potential.

All WOCBP must have a negative pregnancy test within 72 hours prior to receiving the first dose of the investigational agent(s). If the pregnancy test is positive, the patient must not receive protocol treatment and must not be enrolled in the study.

WOCBP is defined as follows: Any female who has experienced menarche and who has not undergone successful surgical sterilization (hysterectomy, bilateral tubal ligation, or a bilateral oophorectomy) or is not postmenopausal (defined as amenorrhea > 12 consecutive months, or women on hormone replacement therapy (HRT) with documented plasma follicle-stimulating hormone (FSH) level > 35 mIU/ml). Even women who are using oral, implanted, or injectable contraceptive hormones or mechanical products (diaphragm, condoms, spermicides) to prevent pregnancy or practicing abstinence or where partner is sterile (e.g. vasectomy), should be considered to be WOCBP.

